8.3 Secondary outcome statistics

The clinically-related objective for this trial is the healing rate of the foot ulcers, as assessed by tracing the wound using a Coloplast measuring grid, or an equivalent performance-equal measuring tool.

The average difference between time points and baseline (week 0) will be calculated per group, 12 weeks being the primary endpoint but weeks 3, 6 and 9 will also be analysed. To compare the groups, the Mann-Whitney U-test will be applied (data will be tested for normal distribution and if applicable, t-test will be applied).

The average change in healing at 12 weeks between the Natrox cohort and the control cohort within the study will be compared using the Mann-Whitney U-test or, if data normally distributed, t-test. Application of this analysis will depend on sample size of control cohort.

The average baseline demographics for participants in each group (Natrox and control) will be described and compared to ascertain the distribution of participants' data for: sex, age, HbA1c level, baseline wound size (cm2), PUSH score, SINBAD DFU grading score (if applicable), EQ5-5D-5L score, CWIQ score, duration of wound (weeks), neuropathy status, ischaemia status.

Other clinical parameters will be recorded too, since they are known to be significantly associated with non-healing of foot ulcers: diabetes status, peripheral arterial disease, heart failure, pretibial oedema (Prompers et al, 2008)

The Chi-squared test will be applied to the above cross-tabulation to determine if there is a significant difference in distribution of treatment outcome in terms of 'status wound healed' (Natrox vs control).

To evaluate the wider effects of the Natrox topical oxygen therapy regime on foot ulcer healing, the following parameters will be compared (median difference between week 0 and different follow-up time points):

- PUSH score
- SINBAD grading score
- Visual analogue pain score
- EQ5-5D-5L score
- CWIQ score

To compare, Mann-Whitney U-test between cohorts, since data is ordinal.

The sample size in this feasibility trial is too small to conduct Cox proportional hazards regression analysis to investigate the role of the dressing regime choice and other in wound healing rates.

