2. INTRODUCTION

The occurrence of foot ulcers has enormous cost complications. Figures available for diabetic foot ulcers (DFU) alone total £650 million per year once associated morbidity is taken into account (NHS Diabetes report). In the UK alone, 169,000 diabetic foot ulcers (DFU) occur every year (Guest et al, 2015). The International Diabetes Federation (2005) reported that up to 70% of all leg amputations happen to people with diabetes and 85% are preceded by a foot ulcer. Furthermore, three quarters of diabetics who experience an amputation will die within five years (Schofield et al, 2006). Diabetes NHS (2012) estimates total National Health Service (NHS) spending on ulceration and amputation in people with diabetes in England in 2010/11 was circa 0.7% of the budget and warned as diabetic numbers grow so will this expenditure. Lipsky et al (2004, 2012) associated infection in DFU with high mortality, high attendance at clinics and possible risk of amputation, advising antibiotics are required for infected wounds, but there is no evidence to support issuing antibiotics for uninfected ulcers. This is a critically important topic, since the longer that healing is delayed, the higher the risk of infection developing (Hampton and Collins, 2005; Grothier, 2015). To further illustrate the point concerning the impact of foot ulcers: the healing rate of DFUs is poor; on average, 24% of wounds have healed by week 12 of treatment, and only 31% at 20 weeks of treatment (Margolis, 1999). A cohort study involving 31 diabetic patients determined that the average healing time for neuropathic DFUs is 78 days whereas this increases to 133 days for patients with additional peripheral vascular disease (Zimny et al, 2002). Further analysis has shown that the size of the ulcer negatively correlates to the healing rate, whereas a patient's age, sex, or type of diabetes is not associated with a change in healing rate outcome (Oyibo, 2001). DFU healing progress at 4 weeks of treatment is a predictor of the likelihood that the wound will be healed by 12 weeks of treatment. If the wound has not healed by at least 50% after 4 weeks, the likelihood that the DFU will be completely healed by 12 weeks is reduced to circa 10% (Sheehan, 2003). Taken together, there is a major group of patients with DFU -those with larger ulcers, and co-morbidities, responding poorly to standard treatment in the first 4 weeks - that is at risk of ending up with long-term wounds taking over 3 months to heal, if at all. Therefore, enhancement of foot ulcer healing rate is desirable to minimise morbidity and healthcare costs.

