6. SUBJECTS

6.1 Anticipated number of research subjects

This concerns a feasibility trial, and therefore the results from this study should inform a potential effect size for Natrox oxygen therapy, and also the degree in variance in wound healing rates (primary clinical outcome). To date, there is not sufficient published data to gain an insight in the effect that Natrox may have on foot ulcer healing. Hayes et al (2017) previously conducted a pilot study involving 10 DFU patients. In that study, there was no screening phase and Natrox treatment lasted for eight weeks. At the week 8 time point, a mean healing vs baseline of 51% was achieved.

Guidance from a publication by Julious (2005) advises the use of 12 participants per treatment arm, and this approach will be taken here (see Table 3). Patient withdrawal rates before week 12 are not known at present and measuring this will be a primary aim

Table 3, sample size numbers required, based on hypothetical differences between published data and study outcomes

	Standard (control) arm	care	Standard care plus Natrox oxygen therapy arm
Patients (n)	12		12

Since this concerns a randomised controlled trial, albeit in the shape of a feasibility study, reprting will be done in line with CONSORT guidelines (Schulz, Altman & Moher 2010). The number of patients screened but who did not meet the inclusion criteria or who declined to participate will be recorded, as will any patients who are lost to follow-up (Appendix 2).

Since this study involves a screening period, after which patients may not qualify for Natrox intervention, it is anticipated that more than 20 patients will be recruited. The patient attrition rate (withdrawal and loss to follow-up) will also be recorded, since this involves a study with at multiple visits, albeit incorporated into standard clinical appointments. Patients will be recruited from the adult (age 18+) population routinely seen by the evaluating clinical staff members.

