6.1.1 Randomisation

Following written consent at -4 weeks, participants will be observed for four weeks to establish healing rate. At the end of four weeks, patients are only eligible for the intervention phase if their wound has healed <50% in the preceding four weeks. At this point, week 0, participants are allocated at random to the control or Natrox intervention group, using a randomised sequence from the freeware randomisation programme, see https://www.randomizer.org/. The randomisation is stratified for ulcer size, with PUSH score of 5 or less, and 6 or above as the cut-off. This size has been determined as the average size of a presenting foot ulcer previously (Zimny et al, 2002).

Sequential envelopes with each next randomisation allocation will be used to achieve concealment and these will be kept in the research department. The researcher will then inform the regular healthcare professional for the participant in question, and the participant themselves, which treatment they've been allocated to. The researcher will dispatch a Natrox device to the clinic where the participant will be seen. At this stage the continuous Natrox treatment (though disconnection for washing or changing of clothes is allowed) will commence.

As the study involves administration of a visible device, it is not possible to achieve blinding for the participants nor the researchers – it is recognised that this increases the risk of bias. Since the device has an indicator to show it is functioning, applying a sham device is not possible either on this occasion.

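### The week-12 healing comparison leaves out the stratification factor and week-0 ulcer size, and lets a normality check on about 12 values per arm pick the test; one adjusted analysis named in advance would be more precise if size is prognostic.

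*Protocol*

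**What the plan says.** Protocol section 6.1.1 sets the allocation: "The randomisation is stratified for ulcer size, with PUSH score of 5 or less, and 6 or above as the cut-off". The Introduction gives a reason to care about size: in the cited literature on diabetic foot ulcers, "the size of the ulcer negatively correlates to the healing rate".

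Section 5.6.2 defines the main clinical outcome as % change in ulcer area from week 0. Section 8.3 makes week 12 the main time point and describes the comparison as an average difference from week 0. The test rule is: "the Mann-Whitney U-test will be applied (data will be tested for normal distribution and if applicable, t-test will be applied". The same rule is repeated for the week-12 comparison and followed by: "Application of this analysis will depend on sample size of control cohort". No stratum, covariate, normality test or significance level is named.

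For healed status, section 8.3 says "The Chi-squared test will be applied to the above cross-tabulation", the aim being "to determine if there is a significant difference in distribution of treatment outcome". The Introduction notes that if a diabetic foot ulcer has not healed by half in four weeks, "the likelihood that the DFU will be completely healed by 12 weeks is reduced to circa 10" per cent. Such slow-healing wounds are what section 6.1.1 selects for randomisation.

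The sample size is a pilot rule of thumb that "advises the use of 12 participants per treatment arm, and this approach will be taken here". Efficacy is a secondary objective, although section 8.2 lets it inform the decision on a larger trial and allows that a large effect might settle the question.

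**The concern.** The design balances the arms on a factor that the protocol treats as prognostic, and the analysis then makes no use of it. With 24 patients, precision is scarce. Week-0 area and PUSH group are collected anyway, so using them costs almost nothing.

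Three features of section 8.3 leave the analysis less fixed than it should be. A normality check on about 12 values per arm decides between a comparison of means and a comparison of ranks, so the reported effect measure is unknown in advance. The week-12 comparison depends on control-arm size with no threshold given. Healed status is to be tested with a large-sample method although very few healed wounds may be seen.

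At stake are the width of the interval around the healing effect and the weight that section 8.2 lets that result carry.

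**Working it through.** **Plan's own figure.** 12 + 12 = 24 agrees with the stated total. No alpha, power, effect size or SD is given, so there is no power figure to reproduce. Assumed below: two-sided 5%, a standardised effect d = 1.0, and a share R² of outcome variance explained by size, varied because the protocol gives only the direction of the relation.

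**Unadjusted power, normal approximation.** Power = Φ(d√(n/2) − 1.96). With n = 12 and d = 1.0: Φ(2.449 − 1.96) = 0.69. It is 0.23 at d = 0.5, 0.50 at d = 0.8 and 0.84 at d = 1.2.

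**Effect of adjusting.** Simulation with 12 per arm, two size strata of 12, balanced 6:6, normal outcome and 6,000 runs per case. The planned test is a Shapiro-Wilk check choosing t-test or Mann-Whitney. The adjusted model has arm, stratum and continuous week-0 size.

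| R² | Power planned | Power adjusted | Type I planned | Type I adjusted |
|---|---|---|---|---|
| 0 | 0.644 | 0.625 | 0.053 | 0.050 |
| 0.1 | 0.644 | 0.672 | 0.042 | 0.050 |
| 0.2 | 0.642 | 0.712 | 0.036 | 0.052 |
| 0.3 | 0.651 | 0.770 | 0.028 | 0.045 |
| 0.5 | 0.659 | 0.892 | 0.018 | 0.050 |

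The change is −2, +3, +7, +12 and +23 points. A correlation of 0.5 is R² = 0.25, so about 10 points.

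**Why the planned test is conservative here.** With balanced strata, the arm difference is free of between-stratum variation, but the unadjusted standard error still includes it. In this simulation the stratum carries 2/π = 0.637 of the variance in size. At R² = 0.3 that is 0.637 × 0.3 = 0.191 of outcome variance, so the effective critical value is 1.96/√(1 − 0.191) = 2.18 and the error rate about 0.029, matching the simulated 0.028.

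**If the list does not balance arms within strata.** Section 6.1.1 states no blocking. Unblocked, the planned test's type I error is 0.046 to 0.052. Adjustment still gains at R² = 0.3 (0.645 to 0.764), but costs more at R² = 0 (0.653 to 0.608).

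**Pre-test alone.** With no prognostic stratum, overall type I error is 0.044 to 0.055 over normal, t3, exponential, log-normal and capped %-healing outcomes (10,000 runs each). For the three skewed shapes, the t-test rejects 0.08 to 0.20 of the time among samples that pass the check, but only 8% to 25% of samples pass.

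**With healed wounds.** Balanced strata, 1 SD effect, 10% of controls at zero area:

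| r | Planned | ANCOVA of log(area + constant) | Rank-based ANCOVA |
|---|---|---|---|
| 0.3 | 0.61 | 0.59 | 0.63 |
| 0.5 | 0.59 | 0.64 | 0.68 |

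Rank-based adjustment gains 2 and 9 points. For comparison, a simulation on a log-normal area ratio, which never reaches zero, gave 62% against 67% at r = 0.3 and 63% against 75% at r = 0.5: 5 and 12 points.

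**Healed status.** Expected healed controls: 12 × 0.10 = 1.2. With equal arms and m healed in total, the expected cells are m/2 and (24 − m)/2, so all reach 5 only for m from 10 to 14. For 0/12 against 4/12, uncorrected χ² = 24 × (12 × 4)²/(12 × 12 × 4 × 20) = 4.8, p = 0.028. With Yates' correction χ² = 2.7, p = 0.100; Fisher's test gives p = 0.093. Section 8.3 does not say which chi-squared version applies. The exact type I error at healing rates of 10%, 24% and 50% is 1.5%, 4.3% and 6.4% for uncorrected chi-squared, and 0.2%, 1.5% and 2.3% for Fisher.

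**The case against.** The strongest reply is that efficacy is secondary in a 24-patient feasibility trial with no alpha or power set, and that covariates are commonly left to an analysis plan, which may exist. That limits the weight of the point. It does not remove it, because section 8.3 names the tests itself and the comment is on what it prescribes.

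A reader might infer several stronger things that the protocol does not support:

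- **That the pre-test gives a wrong error rate or wastes power.** Overall error stays near 5%, and the two-stage rule has slightly more power than Mann-Whitney alone (0.644 against 0.604 at R² = 0). The case against the pre-test is that method and effect measure are not fixed.
- **That type I error is surely too low.** This needs balance within strata, which section 6.1.1 does not state.
- **That week-0 size is ignored.** It enters through the % change; only adjustment is missing.
- **That a large power gain is assured, or that ANCOVA of log area is the clear remedy.** The correlation is assumed, and zero-area wounds make the log model depend on an arbitrary constant.
- **That the control-cohort sentence invites reporting by result.** It conditions on accrual, not outcome. It is vague, which is reason enough to remove it.
- **That the variance handed to the next trial would be inflated.** An SD can be estimated separately from the test, and none is specified.
- **That Fisher's test is the natural substitute for chi-squared.** It is more conservative still.

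The mix of % change and average difference across sections reads as loose wording.

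**Conclusion.** The point holds as a matter of precision and pre-specification, not of an inflated error rate. With 12 per arm and an assumed 1 SD effect, accounting for stratum and week-0 size ranges from a small loss when size is not prognostic to roughly 10 power points at a correlation of 0.5, and tends to gain less when some wounds close completely. The gain rests on a correlation that the protocol asserts in direction only, for diabetic ulcers, while the trial also admits other foot ulcers. The figure of about 1 healed control in 12 likewise assumes that the circa 10% rate carries over. The change is worth making because it is nearly free and because section 8.2 allows the efficacy result to carry weight.

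**What to change.** In section 8.3:

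1. Name one analysis of % area change at week 12 that accounts for PUSH stratum and week-0 area and tolerates zero-area wounds. Rank-based ANCOVA on arm, stratum and week-0 area does this. A van Elteren test stratified by PUSH group is simpler but does not use week-0 area within strata. Report an effect estimate with a 95% CI.
2. Delete the normality pre-test in both places, and the sentence making the analysis depend on control-cohort size.
3. For healed status, replace chi-squared with the risk difference and an exact 95% CI, plus an unconditional exact test (Boschloo) if a p-value is wanted.
4. State that these analyses are secondary and supportive.

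The cost is rewording and up to 2 degrees of freedom, with no new data. If size proves not to be prognostic, about 2 power points are lost with balanced strata, and 4 to 5 in the unblocked simulation.

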Primary objective / outcome measures	To assess the feasibility of conducting a full RCT in the future - Participants' experience of and compliance with Natrox oxygen therapy - Recruitment and attrition rates, willingness of patients to consent and to be randomised, response rates to questionnaires, and degrees of missing data - Testing of eligibility criteria and ability/willingness of clinical staff to partake in recruitment and follow-up of participants - Adequacy of duration of follow-up (e.g. in relation to foot ulcer healing) - Appropriateness of inclusion/exclusion criteria and outcomes measures (both clinical and patient-reported). Descriptive assessment of wound size and characteristics (wk 0,3,6,9,12) Percentage 'wound healed' vs week 0 Percentage healing of the wound vs week 0 Change in semi-quantitative PUSH ulcer size score vs week 0 - SINBAD score (DFU only) vs week 0 - Wound closure status - Clinical characterisation of wound (erythema, purulence, odour, patient-reported pain) Safety of applied oxygen therapy in comparison to standard care arm (ongoing): - Wound infection incidence - Need for secondary interventions, such as surgery				
Secondary objectives / outcome measures					

	Patient-reported outcome measures (wk 0, 6, 12) - (Wound related) Quality of life scores (EQ-5D-5L and CWIQ) - Wound pain scale
Patient population	A total of 24 eligible participants will be randomised to receive either standard care or standard care plus Natrox topical oxygen therapy. Patients to be aged eighteen or over, with measurable foot ulcer present for at least two weeks, treated in podiatry clinic. Participants must have the capacity to provide informed written consent and complete patient reported outcome measures, and be willing and capable to wear the Natrox device.
	All participating patients – whose index wound has not healed by 50% or more in first four weeks of screening whilst in the study and under care of podiatry team - will be randomised for the trial phase. Those patients who were enrolled and whose foot ulcer healed 50% or more complete the study at the end of the four-week screening phase.
	In summary, of those participants whose wound does not heal 50% in four-week screening phase: - 12 Patient will receive treatment as usual (TaU) - 12 Patients will receive TaU plus adjunct Natrox topical oxygen therapy
	Randomisation will be stratified for ulcer size, with cut-off PUSH score of up to and including 5, and 6 and above.

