6.2 Eligibility criteria

6.2.1 Inclusion criteria

- Clinical diagnosis of a Foot Ulcer, present on area that is measurable with a grid sheet (this can include plantar, calcaneus, dorsal, hallux, apex, or ankle based ulcers). This includes DFU, peripheral arterial disease related wound, or other aetiology.
- Minimum chronicity of 2 weeks applicable for the index foot ulcer.
- Adult patients aged ≥ 18 years
- Patients with recurrent wounds, including multiple wounds, are eligible. The largest of the wounds, that is measurable with a grid sheet, will be selected for the trial.
- Mental capacity to give consent

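### Section 8.3 fixes a chi-squared test for wound healed with 12 per arm and no small-count alternative, although only about 1 to 4 healed wounds per arm are likely; the p-value is unreliable, though not invalid

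*Protocol*

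**What the plan says.** Protocol section 8.3 handles the binary healing outcome in one sentence: "The Chi-squared test will be applied to the above cross-tabulation to determine if there is a significant difference in distribution of treatment outcome". The sentence goes on to name the outcome (wound-healed status) and the comparison (Natrox against control). It gives no continuity correction, exact alternative or rule for small counts. The text just before it lists baseline demographics and prognostic factors; no table of arm by healing appears there.

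The numbers that bear on the test are elsewhere in the protocol:

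- Sample size, Research Protocol Summary: "A total of 24 eligible participants will be randomised to receive either standard care or standard care plus Natrox topical oxygen therapy". Section 6.1 takes the figure from a pilot-trial rule of thumb that "advises the use of 12 participants per treatment arm, and this approach will be taken here".
- Selection, section 6.1.1: "patients are only eligible for the intervention phase if their wound has healed <50% in the preceding four weeks".
- Prognosis of such wounds, section 2: if a diabetic foot ulcer has not healed by at least half after 4 weeks, "the likelihood that the DFU will be completely healed by 12 weeks is reduced to circa 10" per cent.
- Prognosis of unselected diabetic foot ulcers, section 2: "on average, 24% of wounds have healed by week 12 of treatment".
- Population, section 6.2.1: "This includes DFU, peripheral arterial disease related wound, or other aetiology".

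**The concern.** The chi-squared test relies on a large-sample approximation, usually trusted when every expected cell count is at least 5. The trial enrols few patients and selects wounds that are unlikely to close, so the healed cells will probably fall short of that. Different versions of the test can then disagree about the same table.

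The protocol is alert to sample size elsewhere in section 8.3: it gives a distribution-based choice of test for the continuous outcome and rules out Cox regression as too ambitious. The binary outcome gets no such provision.

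At stake is how a small difference in closure would be reported. Section 8.2 lets the efficacy results inform whether a larger trial is indicated, and allows that a large enough effect might settle effectiveness. A significance verdict that turns on an unstated software option is a weak basis for either use.

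**Working it through.** **Inputs.** 12 per arm (Summary, section 6.1). Healing of 10% for slow-healing diabetic ulcers and 24% for unselected ones (section 2). Assumed here because the protocol gives no figure: two-sided alpha of 0.05, Natrox healing rates of 30% to 60%, and 10 or 9 assessed per arm if patients drop out.

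**The plan's own figure.** 2 × 12 = 24 reproduces. It is a rule of thumb; no power calculation stands behind the chi-squared test.

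**Expected healed count per arm** = n × pooled healing proportion.

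| Control / Natrox | Calculation | Expected healed per arm |
|---|---|---|
| 10% / 10% | 12 × 0.10 | 1.2 |
| 24% / 24% | 12 × 0.24 | 2.9 |
| 10% / 30% | 12 × 0.20 | 2.4 |
| 10% / 40% | 12 × 0.25 | 3.0 |
| 10% / 50% | 12 × 0.30 | 3.6 |
| 10% / 60% | 12 × 0.35 | 4.2 |

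With 10 or 9 per arm the first row becomes 1.0 or 0.9. For the expected healed count to reach 5 in each arm, at least 10 of 24 wounds must heal. At 10% healing that has a probability of about 0.005%.

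**What the test can do at 10% healing.** The chance that nobody heals, so that the statistic is undefined, is 0.9^24 = 8%. The chance of 3 or fewer healed is 79%; even the most extreme such split, 0 v 3, gives an uncorrected p of 0.064, so significance is out of reach.

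**One table by hand: 0/12 v 4/12.** The cross-product difference is 0 × 8 − 12 × 4 = −48, and the product of the margins is 12 × 12 × 4 × 20 = 11,520.

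- Uncorrected: 24 × 48² / 11,520 = 4.80, p = 0.028.
- Yates: 24 × (48 − 12)² / 11,520 = 2.70, p = 0.100.
- Fisher: 2 × C(12,4) / C(24,4) = 2 × 495 / 10,626 = 0.093.
- Boschloo, computed numerically: 0.045.

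**Further tables.**

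| Healed | Uncorrected | Yates | Fisher | Boschloo | Smallest expected count |
|---|---|---|---|---|---|
| 0 v 4 | 0.028 | 0.100 | 0.093 | 0.045 | 2.0 |
| 1 v 6 | 0.025 | 0.072 | 0.069 | 0.029 | 3.5 |
| 2 v 7 | 0.035 | 0.092 | 0.089 | 0.042 | 4.5 |
| 3 v 8 | 0.041 | 0.101 | 0.100 | 0.064 | 5.5 |

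**True size**, by enumerating all 13 × 13 = 169 tables with the same healing rate in both arms and summing the probability of those with p ≤ 0.05:

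| Healing rate | Uncorrected | Yates | Fisher | Boschloo |
|---|---|---|---|---|
| 10% | 1.5% | 0.25% | 0.25% | 1.5% |
| 24% | 4.3% | 1.5% | 1.5% | 4.2% |
| 40% | 5.9% | 2.1% | 2.1% | 4.2% |
| 50% | 6.4% | 2.3% | 2.3% | 3.8% |
| Maximum | 6.4% | 2.3% | 2.3% | 4.5% |

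The uncorrected test and Boschloo reach different decisions only at 3 v 8 and 4 v 9 and their mirror images.

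**The case against.** A reader might infer that the p-value is simply invalid, or that false positives will be inflated where counts are smallest. The calculations do not support that. At 10% healing the uncorrected test is conservative. Its size passes 5% only at healing rates above 30%, where expected counts are about 4 to 6, and the excess is at most 1.4 percentage points. In every table with an expected count below 5 it reaches the same decision as Boschloo. The large disagreement is with Fisher and Yates, and Fisher is further from the nominal 5% than the test being criticised. The 3 v 8 table meets the minimum of 5, so its discrepancy cannot be blamed on small counts.

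It would also be too strong to say that the protocol expects about one healed wound per arm. The 10% is a published figure for diabetic ulcers on standard treatment, the trial admits other ulcers, and section 6.1 says the published data are not sufficient to judge what effect Natrox may have. A count near 1 requires both arms to heal at about 10%.

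Nor is the comparison undefined: the sentence names both outcome and arms, and the section makes 12 weeks its primary time point. Only the reference to a preceding table misfires.

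Finally, this is a secondary outcome in a feasibility trial, section 5.6.2 measures the main clinical outcome as percentage change in ulcer area, and a correction or exact fallback could sit in an analysis plan that is not shown. All of this stands and limits the weight of the point. It does not remove it: the protocol has already chosen the test, and its wording admits both the uncorrected and the corrected version, which can give opposite verdicts.

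**Conclusion.** The point holds as a modest, inexpensive improvement. Section 8.3 commits to a large-sample test where about 1 to 4 healed wounds per arm are likely, and does not say which version. The resulting p-value is unreliable rather than invalid: true size 1.5% at 10% healing and 6.4% at worst, with the conclusion for a table such as 0/12 v 4/12 depending on the version used (0.028, 0.100, 0.093 or 0.045).

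This rests on 12 assessed per arm, a two-sided 5% level that the protocol does not state, control healing between the quoted 10% and 24%, and Natrox healing of up to 60% alongside control at 10%. If healing in both arms were near 40% or above, expected counts would approach or pass 5 and the small-count argument would fall away; the slight excess over 5% in the uncorrected test would remain.

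**What to change.** Replace the chi-squared sentence in section 8.3 with three elements:

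1. The number and percentage of wounds closed at week 12, by arm, among all randomised.
2. The risk difference, Natrox minus control, with a Newcombe or exact 95% confidence interval.
3. If a p-value is wanted, one exact test named in advance. Boschloo is preferable: its size stays at or below 5%, while Fisher is very conservative here (0.25% at 10% healing, 2.3% at most).

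Replace the pointer to a preceding cross-tabulation with an explicit definition: arm by closed/not closed at week 12.

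The cost is a sentence or two of text. The p-value will usually be slightly larger than the uncorrected one, and at 3 v 8 or 4 v 9 a nominally significant result would no longer be so. In return the trial reports an effect estimate with its uncertainty, which is what planning a larger trial needs.
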